### 2.3.2. Benefit Assessment

While PF-07081532 is not expected to provide any significant long-term clinical benefit to the healthy, overweight or obese participants in this relatively short-term study, potential benefits may include weight loss, receiving medical evaluations/assessments associated with clinical study visits (eg, physical examinations, ECGs, labs), and contributing to the process of developing a potential new therapy for T2DM and obesity.

More detailed information about the known and expected benefits and risks and reasonably expected AEs of PF-07081532 may be found in the IB, which is SRSD, for this study.

### 2.3.3. Overall Benefit/Risk Conclusion

Taking into account the measures to minimize risk to study participants, the potential risks identified in association with PF-07081532 are justified by the anticipated benefits that may be afforded to participants who are overweight or obese.

## 3. OBJECTIVES AND ENDPOINTS

Objectives	Endpoints
Primary:	Primary:

 
To estimate the effect of MD itraconazole on the single-dose PK of PF-07081532 in otherwise healthy, overweight or obese participants.
 
	
 
PF-07081532 PK parameter: AUCinf (if data permita otherwise AUClast)
 

 
To estimate the effect of SD cyclosporine on the single-dose PK of PF-07081532 in otherwise healthy, overweight or obese participants.
 
	
 
PF-07081532 PK parameter: AUCinf (if data permita otherwise AUClast)
 

Secondary:	Secondary:

 
To evaluate the safety and tolerability of PF-07081532 administered separately and in combination with itraconazole or cyclosporine in otherwise healthy, overweight or obese participants.
 
	
 
Assessment of TEAEs, clinical laboratory abnormalities, vital signs, body weight, and ECG parameters.
 
Assessment of mental health as determined by C-SSRS and PHQ-9.
 

 
To evaluate the effects of itraconazole or cyclosporine on additional PK parameters for PF-07081532.
 
	
 
Additional plasma PK parameters for PF-07081532: Cmax and Tmax; and CL/F, Vz/F, t1/2, as data permit.
 

a. Should it be deemed that too few AUCinf estimates (eg, less than 12 for a single treatment) are obtained from the evaluable participants, AUClast may be selected as the primary endpoint for CSR reporting.

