### 9.3.1.2. Statistical Methods for PK Data

Natural  $\log_e$  transformed  $AUC_{inf}$  of PF-07081532 administered without cyclosporine or coadministered with cyclosporine will be analyzed using a mixed effect model with treatment as a fixed effect and participant as a random effect. Estimates of the adjusted mean differences (Test/Reference) and corresponding 90% CIs will be obtained from the models. The adjusted mean differences and 90% CIs for the differences will be exponentiated to provide estimates of the ratio of adjusted geometric means (Test/Reference) and 90% CIs for the ratios. The test treatment will be ‘PF-07081532 40 mg single dose and cyclosporine’ (Period 2), which will be reported separately in comparison to the reference treatment of ‘PF-07081532 40 mg single dose without cyclosporine’ (Period 1).

Natural  $\log_e$  transformed  $AUC_{inf}$  of PF-07081532 administered without itraconazole or coadministered with itraconazole will be analyzed using a mixed effect model with treatment as a fixed effect and participant as a random effect. Estimates of the adjusted mean differences (Test/Reference) and corresponding 90% CIs will be obtained from the models. The adjusted mean differences and 90% CIs for the differences will be exponentiated to provide estimates of the ratio of adjusted geometric means (Test/Reference) and 90% CIs for the ratios. The test treatment will be ‘PF-07081532 40 mg single dose and itraconazole’ (Period 3), which will be reported separately in comparison to the reference treatment of ‘PF-07081532 40 mg single dose without itraconazole’ (Period 1).

PK parameters, including plasma  $AUC_{inf}$ ,  $AUC_{last}$ ,  $C_{max}$ ,  $T_{max}$ , and  $CL/F$ ,  $V_z/F$ ,  $t_{1/2}$ , as data permit, of PF-07081532 will be summarized descriptively by treatment. For  $AUC_{inf}$ , a listing of the individual participant ratios (Test/Reference) will be provided. Box and whisker plots for  $AUC_{inf}$  will be plotted by treatment.

The plasma concentrations of PF-07081532 will be listed and descriptively summarized by nominal PK sampling time and treatment. Individual participant, as well as mean and median profiles, of the plasma concentration-time data will be plotted by treatment using actual (for individual) and nominal (for mean and median) times, respectively. Mean and median profiles will be presented on both linear and semi-log scales.

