#### 9.4. Interim Analyses

No interim analysis will be conducted for this study. As this is an open-label study, the sponsor may conduct unblinded reviews of the data during the course of the study for the purpose of safety and PK assessments.

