#### 9.5. Sample Size Determination

Approximately 16 participants will be enrolled in the study such that approximately 12 evaluable participants complete the study.

A sample size of 12 participants will provide adequate precision to estimate the relative bioavailability of PF-07081532. The following table presents the width of 90% CI for different estimated effects, with 80% coverage probability.

Parameter	Estimated Effect (100*Test/Reference)	90% CI		CI Width
AUC inf	85%	66.46%	108.71%	42.25%
	90%	70.37%	115.11%	44.74%
	95%	74.28%	121.50%	47.22%
	100%	78.19%	127.90%	49.71%
	105%	82.10%	134.29%	52.20%
	110%	86.01%	140.69%	54.68%
	115%	89.92%	147.08%	57.17%

These estimates are based on the assumption that within-participant standard deviation is 0.291 for  $\ln AUC_{inf}$  as obtained from study C3991001.

Participants who withdraw from the study or discontinue treatment, or whose PK samples are considered to be non-evaluable with respect to the primary PK objective may be replaced at the discretion of the investigator upon consultation with the sponsor. For participants who remain in the study, the SAP will address PK data associated with episodes of vomiting following administration of study intervention and/or missed doses for any of the study interventions.

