6. ANALYSES AND SUMMARIES

6.1. Primary Endpoints

Natural log_e transformed AUC_{inf} (if data permit, otherwise AUC_{last}) of PF-07081532 administered without cyclosporine or coadministered with cyclosporine will be analyzed using a mixed effect model with treatment as a fixed effect and participant as a random

effect. Estimates of the adjusted mean differences (Test/Reference) and corresponding 90% CIs will be obtained from the models. The adjusted mean differences and 90% CIs for the differences will be exponentiated to provide estimates of the ratio of adjusted geometric means (Test/Reference) and 90% CIs for the ratios. The test treatment will be 'PF-07081532 40 mg singe dose and cyclosporine' (Period 2), which will be reported separately in comparison to the reference treatment of 'PF-07081532 40 mg singe dose without cyclosporine' (Period 1).

Natural log_e transformed AUC_{inf} (if data permit, otherwise AUC_{last}) of PF-07081532 administered without itraconazole or coadministered with itraconazole will be analyzed using a mixed effect model with treatment as a fixed effect and participant as a random effect. Estimates of the adjusted mean differences (Test/Reference) and corresponding 90% CIs will be obtained from the models. The adjusted mean differences and 90% CIs for the differences will be exponentiated to provide estimates of the ratio of adjusted geometric means (Test/Reference) and 90% CIs for the ratios. The test treatment will be 'PF-07081532 40 mg singe dose and itraconazole' (Period 3), which will be reported separately in comparison to the reference treatment of 'PF-07081532 40 mg singe dose without itraconazole' (Period 1).

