7. INTERIM ANALYSES

No formal interim analysis will be conducted for this study. As this is an open-label study, the sponsor may conduct unblinded reviews of the data during the course of the study for the purpose of safety assessment, facilitating PK modeling, and/or supporting clinical development.

Final analysis will follow the official database release. As this will be an open-label study, there is no formal unblinding of the randomization code.

APPENDICES

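### Does the discretionary switch from AUCinf to AUClast, with fewer than 12 estimates as its only guide, need a binding rule?

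*Protocol*

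**What the plan says.** The same footnote stands in the protocol synopsis, protocol Section 3 and SAP Section 2.2. AUCinf is primary for each objective. If it is judged that too few estimates exist ("eg, less than 12 for a single treatment) are obtained from the evaluable participants"), AUClast may be reported as primary instead. The count is an example and the switch is permitted, not required. No decision-maker is named. SAP Section 6.1 models whichever measure is chosen, separately for each comparison.

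Protocol Section 9.5 uses the same number for planning: "Approximately 16 participants will be enrolled in the study such that approximately 12 evaluable participants complete the study", and "A sample size of 12 participants will provide adequate precision". It also says that participants "whose PK samples are considered to be non-evaluable with respect to the primary PK objective may be replaced".

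The trial is open-label. Protocol Section 9.4 says "the sponsor may conduct unblinded reviews of the data during the course of the study for the purpose of safety and PK assessments"; SAP Section 7 gives the "purpose of safety assessment, facilitating PK modeling, and/or supporting clinical development". Protocol Section 9.1 states that no hypothesis is tested.

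On reporting, SAP Section 6.2.2 (Table 2) gives geometric means by treatment for both AUCinf and AUClast, and lists the percentage extrapolated, the fit statistic and the number of terminal points. For AUCinf, "a listing of the individual participant ratios (Test/Reference) will be provided" (protocol Section 9.3.1.2). SAP Section 6.2 applies the same mixed model to further parameters, whose names are redacted.

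**The concern.** The only number attached to the switch equals the number of evaluable participants the trial expects. If the plan is met exactly, one profile without a usable terminal slope is enough to open the option of a different primary measure, although 11 pairs estimate the ratio almost as well as 12. The choice is left to the report stage, in a trial whose PK data may be seen while it runs.

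The two measures need not agree. AUClast stops at the last quantifiable sample, at the latest 120 h in Periods 1 and 2 and 144 h in Period 3. If an inhibitor lengthens the half-life, more of the area falls after that point and AUClast tends to understate the interaction. At stake is whether a reader could trust the primary ratio if the measure had been chosen with both results in view.

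**Working it through.** **1. Precision.** Inputs from protocol Section 9.5: within-participant SD 0.291 on the log scale, 90% CI, 80% coverage probability for the width. For n complete pairs,

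half-width = t(0.95, n-1) × 0.291 × √(2/n) × √(χ²(0.80, n-1)/(n-1)).

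At n = 12: 1.7959 × 0.1188 × 1.1533 = 0.246, giving 78.19 to 127.90% at a ratio of 100%. This reproduces the protocol's table.

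| Pairs | Log half-width | 90% CI at 100% | Change |
|---|---|---|---|
| 12 | 0.246 | 78.2 to 127.9 | – |
| 11 | 0.261 | 77.0 to 129.8 | +6% |
| 10 | 0.278 | 75.7 to 132.1 | +13% |
| 9 | 0.300 | 74.1 to 134.9 | +22% |

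The mixed model also keeps unpaired values, so the true loss is no larger. Precision alone gives no reason to switch at 11. But the plan does not say the number rests on precision, and does not require a switch at 11.

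**2. Chance of meeting the example.** With N evaluable and a probability q that a profile is non-estimable (assumed 1, 2 or 5%, independent), p = P(Binomial(N, 1-q) ≤ 11). For any of three treatments the chance is 1-(1-p)³.

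| Evaluable | q = 1% | q = 2% | q = 5% |
|---|---|---|---|
| 12 | 30% | 52% | 84% |
| 13 | 2% | 8% | 35% |
| 14 | 0.1% | 0.7% | 9% |
| 15 | 0.004% | 0.06% | 1.6% |
| 16 | about 0 | 0.003% | 0.3% |

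The risk is high at exactly 12 and falls quickly above it. Replacement is not counted.

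**3. Is AUCinf likely to be estimable?** Protocol Section 2.2.4.1 gives mean half-lives t from 18.03 to 26.5 h across the two completed studies. With mono-exponential decline the extrapolated share is 2^(-T/(R·t)), where T is the last sampling time and R the factor by which half-life lengthens. Period 1 (T = 120, R = 1): 1.0 to 4.3%. Itraconazole (T = 144, R = 1.45): 2.2 to 7.4%. Cyclosporine, if inhibition lasted all 120 h at R = 1.45: 4.2 to 11.5%. The value 1.45 is 1/(1-0.31): the 31% CYP3A share of hepatic metabolism (Section 2.2.2) fully inhibited, taking hepatic metabolism as all clearance. These shares are modest, so AUCinf should usually be obtained.

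**4. Error if AUClast is used.** In a one-compartment model with concentrations quantifiable to the last sample, the AUClast ratio is R(1-2^(-T/(R·t)))/(1-2^(-120/t)).

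- Itraconazole: error +0.6 to +2.1% at a true 1.0, zero at 1.2 (= 144/120), and -1.2 to -3.3% at 1.45.
- Cyclosporine, sustained inhibition, ignoring carryover: zero at 1.0 and -3.2 to -7.5% at 1.45.

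The periods run without a break and the 120 h sample of Period 1 is the predose sample of Period 2, so carryover belongs in the cyclosporine comparison. The residue is f = 2^(-120/t), or 1.0 to 4.3%, and it multiplies both Period 2 areas by 1+f. At a true 1.45:

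| Half-life | AUCinf error | AUClast error |
|---|---|---|
| 18.03 h | +1.0% | -2.2% |
| 26.5 h | +4.3% | -3.5% |

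For example, at 26.5 h: 1.0433 × (1-0.1148)/(1-0.0433) = 0.965.

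If clearance is instead halved for only 12 to 48 h (assumed), AUClast without carryover errs by -0.04 to -1.3%. With carryover it is slightly closer to the truth than AUCinf at every half-life tried. At 26.5 h and 48 h the errors are +3.0% for AUClast and +4.3% for AUCinf.

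Carryover into Period 3 is smaller, because the PF-07081532 doses of Periods 2 and 3 are 8 days (192 h) apart: 2^(-192/26.5) = 0.7% without inhibition.

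**The case for a change.** The best case for a change is about prespecification. Protocol Section 9.3 leaves the handling of missing data to the SAP, yet the SAP repeats the footnote without a rule. The sponsor may look at PK data during an open-label trial, so the measure could be chosen with both ratios known. A lower binding count would rarely be used and would cost a line of text. Summaries by treatment are not a modelled ratio with a CI, and Section 6.1 supplies that for one measure only. If cyclosporine inhibition lasted the full 120 h and doubled exposure, AUClast would read 1.73 to 1.84 even after carryover is counted.

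Part of this stands. The rule is discretionary, nobody is named to apply it, and 12 is an awkward example.

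The rest is weaker. No better number follows from the documents: there is no margin, test or minimum precision to set it against. The large cyclosporine error needs a doubling of exposure and 120 h of inhibition from a single dose, and nothing in the documents supports that duration. Two-fold exposure with itraconazole lies above the 1.45 ceiling. With complete pairs, the ratio of the two tabulated geometric means is the model's own point estimate, so a reader can compare both measures; at most the second CI is absent. Even that cannot be asserted while the parameter names in SAP Section 6.2 are redacted. The footnote is attached to each objective and Section 6.1 repeats the condition for each comparison, so a switch in one comparison alone is the natural reading, although the shared Period 1 leaves some ambiguity.

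**Conclusion.** No change to the plan follows. This is a loosely worded fallback that analysts can apply sensibly. It permits a switch, and extrapolation and fit diagnostics are listed to inform the judgement. Meeting the example count is likely only if the evaluable number lands on 12 or 13 with some profiles lost; with 15 or 16 it is at most 1.6%, before replacement.

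If the switch were made, the ratio would move by a few percent at plausible interaction sizes: at most about -3.3% for itraconazole, and -2.2 to -3.5% for cyclosporine under sustained inhibition. For cyclosporine AUCinf is not clearly the less biased measure, since carryover raises it by 1.0 to 4.3%. Either error is small beside an interval planned at 78 to 128%, and conclusions under either measure would remain sound.

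This rests on one-compartment kinetics, the documented mean half-lives, concentrations quantifiable to the last sample, a true ratio no greater than about 1.45 where inhibition is sustained, and assumed non-estimability of 1 to 5%. A true cyclosporine ratio near 2 with inhibition lasting 120 h would make the difference larger. Naming who decides, or adding a second modelled CI, would be a courtesy to the reader and is not needed for the trial to answer its question.

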## 4. STUDY DESIGN

### 4.1. Overall Design

This is a Phase 1, open-label, fixed-sequence, 3-period study to evaluate the effect of multiple doses of itraconazole and a single dose of cyclosporine on the single-dose PK of PF-07081532 in otherwise healthy, overweight or obese adult participants. The 3 study periods will be conducted consecutively without a break.

All participants will provide informed consent and undergo Screening evaluations to determine their eligibility. Screening will occur within 28 days of the first dose of study intervention on Period 1 Day 1. Participants who discontinue from the study before completing all assessments may be replaced at the discretion of the investigator and sponsor.

Approximately 16 participants will be enrolled in the study such that approximately 12 evaluable participants complete the study.

The total duration of participation from the Screening Visit to the F/U telephone contact will be approximately 82 days or 12 weeks, approximately 3 weeks of which will be conducted on an inpatient basis. The 21-day inpatient portion of the study will be conducted as follows:

**Period 1:** Days -1 to 5 (Study Days -1 to 5; participants are admitted to the CRU on Day -1), 40 mg SD PF-07081532 on Day 1;

**Period 2:** Days 1 to 5 (Study Days 6 to 10), 40 mg SD PF-07081532 plus 600 mg SD cyclosporine on Day 1;

**Period 3:** Days 1 to 10 (Study Days 11 to 20; participants are discharged from the CRU on Study Day 20), 200 mg itraconazole QD ×9 days plus 40 mg SD PF-07081532 on Day 4.

A telephone F/U contact will occur 28-35 days from the last dose of study intervention (Period 3, Day 9).

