**Table 2. PK Blood Sampling - Periods 1 and 2**

Visit Identifier	Periods 1 and 2																Notes
Period Day	1						2	3	4	5							
Hours After Dose	0	0.5	1	2	4	6	8	10	12	14	24	36	48	72	96	120	
 
Hour 0 = predose sample collection.
 
The 120-hour PK samples in Periods 1 and 2 are the same as the 0-hour PK samples in Periods 2 and 3, respectively.
 

Study intervention administration PF-07081532	X																
Study intervention administration cyclosporine ( Period 2 only )	X																
PK blood sampling PF-07081532	X	X	X	X	X	X	X	X	X	X	X	X	X	X	X	X	

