##### **2.2.4.1. Clinical Pharmacokinetics**

The clinical PK of PF-07081532 in adult participants have been evaluated to date in 2 completed studies (C3991001 and C3991002). The results of these completed studies are summarized in the PF-07081532 IB.

In Study C3991001 following administration of single oral doses of PF-07081532 under fasted conditions to healthy participants, PF-07081532 was absorbed relatively rapidly with a

median  $T_{max}$  of 1.00 to 4.02 hours (individual  $T_{max}$  values ranged between 0.5 and 6 hours). Based on the individual plasma concentration-time profiles, the absorption phase exhibited multiple peaks, especially at the higher dose levels. Mean  $t_{1/2}$  ranged from 18.03 to 20.90 hours across all doses. Plasma  $C_{max}$  increased less than proportionally across the entire investigated dose range (from 10 mg to 200 mg), while plasma  $AUC_{inf}$  increased less than proportionally from 10 mg to 30 mg and approximately proportionally from 30 mg to 200 mg. Inter-participant variability for PF-07081532 exposure was low to moderate and ranged from 9% to 36% CV for  $C_{max}$  and 15% to 44% CV for  $AUC_{inf}$  across all doses. Overall, the results indicate that PF-07081532 may be administered without regard to food.

In Study C3991002 following administration of PF-07081532,  $C_{max}$  was observed at 1 to 2 hours on Day 1, and 2 to 8 hours following the last dose on Day 28 or 42. Across all dose groups, the mean  $t_{1/2}$  ranged from 20.70 to 26.50 hours. PF-07081532 exposure generally increased in an approximately dose-proportional manner across the dose range studied, and accumulation of less than 2.1-fold was observed. Urinary recovery of unchanged PF-07081532 was low, with less than 0.2% of the dose recovered in the 24-hour dosing interval following last dose administration. Interparticipant variability for PF-07081532 exposure ranged from 17% to 51% CV for  $C_{max}$  and 15% to 62% CV for  $AUC_{tau}$  across all doses. No substantial differences in PF-07081532 exposure ( $C_{max}$  and  $AUC_{tau}$ ) were observed between participants with T2DM and obesity either after single dose (Day 1, 10 mg) or multiple dose (Day 28, 120 mg and Day 42, 180 mg) administration.

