In Study C3991003 following single-dose (Day 1) and multiple-dose (Day 42) administration of PF-07081532, peak plasma PF-07081532 concentrations ( $C_{max}$ ) were observed at 1 to 2 hours and 2 to 5 hours, respectively. Terminal  $t_{1/2}$  averaged 24.37 to 26.04 hours following multiple-dose administration (Day 42). PF-07081532 exposure ( $C_{max}$  and  $AUC_{tau}$ ) increased in an approximately dose-proportional manner across the dose range studied. Accumulation with QD dosing was less than 2-fold. No substantial differences were observed in the achieved exposures (both  $C_{max}$  and  $AUC_{tau}$ ) between participants with T2DM and obesity either after single-dose (Day 1, 20 mg) or multiple-dose (Day 42, 60 mg) administration.

Refer to the IB for more details on the clinical PK of PF-07081532.

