**Table 4. Plasma PK Parameters for PF-07081532**

Parameter	Definition	Method of Determination
$AUC_{last}$	Area under the plasma concentration-time profile from time zero to the time of the last quantifiable concentration ( $C_{last}$ ).	Linear/Log trapezoidal method.
$AUC_{inf}^a$	Area under the plasma concentration-time profile from time zero extrapolated to infinite time.	$AUC_{last} + (C_{last}^*/k_{el})$ , where $C_{last}^*$ is the predicted plasma concentration at the last quantifiable time point estimated from the log-linear regression analysis.
$C_{max}$	Maximum plasma concentration.	Observed directly from data.
$T_{max}$	Time for $C_{max}$ .	Observed directly from data as time of first occurrence.

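### Period 2 AUC includes what is left of the Period 1 dose given 120 h earlier, so the cyclosporine ratio is biased upward by about 1-2%, and possibly 3-4%, with no prespecified correction

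*Protocol*

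**What the plan says.** **Timing.** Protocol 4.1 places the first 40 mg dose on Study Day 1 and describes Period 2 as "Days 1 to 5 (Study Days 6 to 10), 40 mg SD PF-07081532 plus 600 mg SD cyclosporine on Day 1". The periods have no gap: "The 3 study periods will be conducted consecutively without a break". The note to Protocol Table 2 confirms the interval and shows that the residual is measured: "The 120-hour PK samples in Periods 1 and 2 are the same as the 0-hour PK samples in Periods 2 and 3, respectively".

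**Half-life.** Protocol 2.2.4.1 gives three sets of means: single doses in healthy participants (C3991001), "ranged from 18.03 to 20.90 hours across all doses"; the repeat-dose study C3991002, "ranged from 20.70 to 26.50 hours"; and C3991003, in T2DM or obesity, "averaged 24.37 to 26.04 hours following multiple-dose administration (Day 42").

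**Derivation and analysis.** Protocol Table 4 defines AUCinf as "Area under the plasma concentration-time profile from time zero extrapolated to infinite time". In SAP 6.1 the log AUC of PF-07081532 "administered without cyclosporine or coadministered with cyclosporine will be analyzed" with treatment as a fixed and participant as a random effect; the SAS code in SAP Appendix 1 matches. SAP 5.3.1 covers values below quantification, missing and anomalous values, dosing errors and vomiting. The readable text has no rule for a predose concentration above zero, and SAP 2.1 declares no change from the protocol analysis.

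**The concern.** The Period 2 profile is the sum of the new dose and the tail of the Period 1 dose, and both are counted in the test AUC. The reference AUC has no such tail. The sequence is the same for everyone, so the error cannot cancel between participants, and no model term absorbs it.

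The cyclosporine ratio is one of the two primary results. Its point estimate and 90% CI are moved upward by an amount that can be foreseen now. A correction chosen later would be weaker evidence than one fixed in advance, because Protocol 9.4 and SAP 7 let the sponsor review the open-label data during the study.

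**Working it through.** **1. The plan's own precision figure.** Protocol 9.5 assumes a within-participant SD of 0.291 and n = 12, and gives 78.19% to 127.90% at an estimated effect of 100%.
- SE = 0.291 × √(2/12) = 0.1188.
- Half-width on the ln scale, with 80% coverage probability = t(0.95, 11 df) × SE × √(χ²(0.80, 11)/11) = 1.796 × 0.1188 × 1.153 = 0.2461.
- 100 × exp(±0.2461) = 78.19% to 127.90%. The other six rows of the table reproduce as well.

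**2. Residual share of the Period 1 dose.** With first-order elimination and linear superposition, the share of AUCinf still to come at 120 h is about f = 2^(−120/t½). If cyclosporine leaves elimination unchanged or lowers clearance, the ratio is multiplied by about 1 + f. The ln bias is ln(1 + f).

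| Mean t½ (h) | Half-lives in 120 h | f | ln bias / 0.2461 | Coverage of the 90% CI |
|---|---|---|---|---|
| 18.03 (single dose, healthy) | 6.66 | 0.99% | 4% | 89.9% |
| 20.90 (single dose, healthy) | 5.74 | 1.87% | 8% | 89.6% |
| 24.37 (multiple dose) | 4.92 | 3.29% | 13% | 88.9% |
| 26.04 (multiple dose) | 4.61 | 4.10% | 16% | 88.3% |
| 26.50 (C3991002 upper value) | 4.53 | 4.33% | 17% | 88.1% |

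Coverage is from the noncentral t with 11 df and noncentrality ln(1 + f)/0.1188. At f = 4.33% the planned limits at 100% move to 78.19 × 1.0433 = 81.6% and 127.90 × 1.0433 = 133.4%. At f = 1.87% they move to 79.7% and 130.3%.

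**3. Check on the actual sampling times.** Noncompartmental analysis of a one-compartment oral profile (assumed ka = 1/h) at the Table 2 times gives a ratio bias of +1.0% to +4.5% over 18.03 to 26.50 h. It is essentially the same for AUClast.

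**4. Check against accumulation.** Protocol 2.2.4.1 reports once-daily accumulation below 2.1-fold (C3991002) and below 2-fold (C3991003). Under linear kinetics, a ratio R means that 1 − 1/R of a single-dose AUC lies beyond 24 h. Carrying that forward another 96 h:
- C3991002: (1 − 1/2.1) × 2^(−96/26.5) = 4.3% at most.
- C3991003: (1 − 1/2) × 2^(−96/24.37) = 3.3%, and at 26.04 h 3.9%, at most.

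The top of the range in steps 2 and 3 is therefore at or slightly above what the accumulation data allow.

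**5. Dependence on mechanism.** In the same simulation, lowering clearance 1.5- or 2-fold leaves the relative bias unchanged, because the residual is slowed along with the new dose. If cyclosporine acts only on bioavailability, the residual is untouched and the bias is f divided by the true ratio. At a true ratio of 2 (assumption) that is 0.5% to 2.2%.

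**6. Itraconazole comparison.** From Study Day 6 to Period 3 Day 4 (Study Day 14) is 8 days = 192 h. 2^(−192/t½) runs from 0.06% at 18.03 h to 0.66% at 26.50 h.

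**The case against.** **The upper end may not apply.** This trial gives isolated single doses, and the half-lives explicitly tied to single doses are 18.03 to 20.90 h. There the gap exceeds 5 half-lives and the bias is 1.0-1.9%. The longer values come from multiple-dose studies. This stands: the documents do not separate the effect of repeat dosing from that of population, so 3-4% is an upper range and not the expected value.

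**A breached washout rule.** A reader might infer that 4.5 half-lives breaks the protocol's own standard of 5. The documents do not support that: the 5 half-lives in Protocol 5.2 is an eligibility rule for prior medicines, not a washout between periods.

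**A constant bias.** A reader might also infer that the estimate is always the true ratio times 1 + f. That requires cyclosporine to act by lowering clearance, and the documents do not establish the mechanism or how long one dose inhibits.

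**A material effect on itraconazole.** A Period 3 residual of about 6% can be produced by assuming that cyclosporine doubles the half-life for 120 h and itraconazole then slows elimination 1.45-fold: 2^(−120/53) × 2^(−72/38.4) = 5.7%. Nothing in the documents supports those inputs.

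**Little practical consequence.** No hypothesis is tested, no no-effect boundary is stated, and a marked interaction would read the same. The SAP also lists concentrations and kel, so a reader could work out the residual. This stands as to importance, but a listing is not a prespecified corrected estimate.

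**Conclusion.** The point holds as a minor, one-directional bias in one primary estimate. The cyclosporine ratio is overstated by about 1-2% at single-dose half-lives and by up to about 3-4% at multiple-dose half-lives. This is 4-17% of the planned CI half-width, with coverage of 88-90% in place of 90%.

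The sizes rest on study-mean half-lives, first-order elimination and linear superposition, with a clearance effect or no effect of cyclosporine; they are smaller if only bioavailability changes. A participant with a longer half-life than the means carries more: 6% at 30 h and 9% at 35 h (assumed values). The material does not show that the conclusion about a marked interaction would change, or that the itraconazole comparison is meaningfully affected. A correction is worth adding because it is cheap and uses a sample already taken.

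**What to change.** Prespecify in SAP 5.3.1 and 6.1 a carryover-corrected analysis of Period 2 AUC, reported beside the planned uncorrected primary analysis:
- Subtract C0 × exp(−kel × t) from each Period 2 concentration, where C0 is the participant's Period 2 predose concentration and kel the terminal rate constant from the same period.
- For AUCinf this is AUCinf − C0/kel. For the AUClast fallback, subtract C0 × (1 − exp(−kel × tlast))/kel.
- List the predose concentration as a percentage of Cmax for each participant.
- State that the correction is approximate if inhibition wanes within the period. With clearance halved for only 24 to 48 h (assumption, one-compartment model), about 0.3% to 1.4% bias would remain.

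Kel should come from Period 2. If clearance is halved for the whole period (assumption), using the Period 1 value leaves 0.5% to 2.5%.

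**Cost.** A few lines of SAP text and programming, and no new samples. Error in estimating kel adds slight noise, and where kel cannot be estimated the correction cannot be made. If the corrected AUC is to become the primary result, Protocol 9 calls for major changes to primary endpoint definitions or their analyses to be reflected in a protocol amendment; reporting it alongside leaves the primary analysis as it is.

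**Separately,** reconcile the Table 2 note, which equates the Period 2 120-h sample with the Period 3 0-h sample, with Table 3. Table 3 places hour 0 on Period 3 Day 4, 192 h after the Period 2 dose; the 120-h point falls on Period 3 Day 1.
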